7.5. Dose Titration Criteria

Dose titration may follow the scheduled dosing regimens described in Section 7.3 or occur due to tolerability concerns.

Dose titrations may involve increases or decreases in dosing frequency and are dependent on tolerability (as assessed by a review of AEs and safety laboratory results). In general, down-titration may be done in response to tolerability concerns and can occur at any time.

Up-titration will be done per protocol based on tolerability, as assessed by the Investigator based on response, or following resolution of a tolerability concern that previously led to down-titration. Up-titrations may only occur to the maximum dose and frequency indicated as defined in [Section 7.3](#).

Scheduled Dose Titration - After initiation of OCA or matching placebo, titration may be considered as early as the Week 12 Visit. Subsequent titrations in dose for patients may occur no earlier than 6 weeks following an up-titration.

Tolerability Dose Titration - Investigators may decrease the dosing frequency or dose as considered clinically appropriate (eg, tolerability).

7.5.1. Pre-Titration Tolerability Assessment Requirements

Tolerability of investigational product must be assessed prior to titrating a patient to a higher dose. To determine if a patient is eligible for a dose titration refer to [Section 7.3](#).

7.6. Close Observation

If investigational product is interrupted or discontinued as described in [Section 8.4](#), patients should be closely monitored (contacted by the site a minimum of every 2 weeks and scheduled visits every 6 weeks; if returning to the site for a scheduled visit is not feasible, use of a local lab may be permissible at the Investigator's discretion). At a minimum, the following assessments should be conducted at each study visit:

- Physical exam and thorough review of patient reported signs and symptoms,
- Liver biochemistry (including ALP, ALT, AST, GGT, total and conjugated bilirubin, creatinine, and albumin), prothrombin time (PT)/INR, serum electrolytes, and assessment of Child Pugh (only if the patient is at the study site) and MELD scores.

In addition, a trough pharmacokinetic sample for assessment of OCA serum drug levels and its major metabolites should be obtained in any patient who develops an AE that is indicative of or consistent with hepatic injury or decompensation.

The following additional monitoring procedures should be performed for events of potential hepatic injury (per FDA Guidance for Industry on Drug Induced Liver Injury) or suspected hepatic decompensation based on criteria described in [Section 7.4.1](#), [Section 7.4.2](#), and [Section 7.4.3](#). These cases need to be discussed with the Sponsor's Medical Monitor:

- Repeating liver biochemistry and function tests as described in [Section 7.4.2](#). Frequency of retesting can decrease to once a week or less if abnormalities stabilize or the study drug has been discontinued and the patient is asymptomatic, as clinically indicated.
- Obtaining a more detailed history of symptoms and prior or concurrent diseases.
- Obtaining a history of concomitant drug use (including nonprescription medications and herbal and dietary supplement preparations), alcohol use, recreational drug use, and special diets is important. Concomitant drugs with potential hepatotoxicity should be recorded and discontinued unless alternative therapies are not available. In the case of concomitant drugs potentially hepatotoxic, continued use of investigational

product should be discussed with the Sponsor's Medical Monitor. The patient may be discontinued from investigational product, if clinically appropriate.

- Obtaining a history of exposure to environmental chemical agents or herbal supplements which may be associated with liver toxicity.
- Ruling out acute viral hepatitis types A, B, C, D (in those thought to have acute HBV infection), and E; autoimmune or alcoholic hepatitis; Wilson's disease, hypoxic/ischemic hepatopathy; and biliary tract disease.
- Investigators should consider testing for Hepatitis E virus when assessing for hepatic decompensation as infection with Hepatitis E virus in patients with chronic liver diseases such as PBC may rapidly worsen with signs and symptoms similar to drug induce liver injury (Kumar 2013)
- Obtaining additional tests to evaluate liver function, as appropriate (e.g., INR, direct bilirubin).
- Seeking hepatology consultation, if the Investigator is not a hepatologist

7.7. Criteria for Study Termination

The Sponsor (Intercept Pharmaceuticals, Inc.) reserves the right to terminate the study at any time. It is normal procedure to review the emerging clinical and safety data. As a result of such a review or a recommendation by the Data Monitoring Committee (DMC), it may be necessary to stop the study before all patients have completed the study. In addition, the Sponsor may terminate the study at an investigational site at any time (eg, Good Clinical Practice [GCP] noncompliance or poorly performing sites, as determined by the number of patients enrolled or the quality of the study data).

The Investigator and/or Sponsor (or designee) must notify the Institutional Review Board/Independent Ethics Committee (IRB/IEC) of discontinuation of a site or the study and the reason for doing so.

Investigators will be informed by the Sponsor as to when the final study visit is to be completed, and should then schedule all patients for the end of study (EOS) or end of treatment (EOT) Visit.

8. SELECTION AND WITHDRAWAL OF PATIENTS

8.1. Patient Population

This study will be conducted at approximately 50 international study sites with experience in treating patients with PBC with moderate to severe hepatic impairment defined as CP-B and CP-C. Prospective patients will be identified primarily from the hospital and/or physician's database of patients with PBC, or may be referred from other physicians. Patients may self-refer to an Investigator if they become aware of the study through local, national, or international PBC patient societies, forums, or networks.

8.2. Patient Inclusion Criteria

1. A definite or probable diagnosis of PBC (consistent with American Association for the Study of Liver Diseases [AASLD] and European Association for the Study of the Liver [EASL] Practice Guidelines [Lindor 2009, EASL 2009]), defined as having ≥ 2 of the following 3 diagnostic factors:
 - History of elevated ALP levels for at least 6 months
 - Positive antimitochondrial antibody (AMA) titer or if AMA negative or low titer ($\leq 1:80$), PBC-specific antibodies (anti-GP210 and/or anti-SP100) and/or antibodies against the major M2 components (PDC-E2, 2-oxo-glutaric acid dehydrogenase complex)
 - Liver biopsy consistent with PBC (collected at any time prior to Screening)
2. Evidence of cirrhosis including at least one of the following:
 - Biopsy results consistent with PBC Stage 4
 - Liver stiffness as assessed by TE Value ≥ 16.9 kPa
 - Clinical evidence in the absence of acute liver failure consistent with cirrhosis including: gastroesophageal varices, ascites, radiological evidence of cirrhosis (nodular liver or enlargement of portal vein and splenomegaly)
 - Combined low platelet count ($< 140\,000/\text{mm}^3$) with:
 - persistent decrease in serum albumin, or
 - elevation in prothrombin time /INR (not due to antithrombotic agent use), or
 - elevated bilirubin ($2 \times$ ULN)
3. Satisfy the criteria of the modified CP classification for hepatic impairment during Screening:
 - Moderate: CP-B (Scores 7 to 9) or
 - Severe: CP-C (Scores 10 to 12)
4. MELD score of 6 to 24 at Screening
5. Age ≥ 18 years
6. Taking UDCA for at least 12 months (stable dose for ≥ 3 months) prior to Day 1, or unable to tolerate or unresponsive to UDCA (no UDCA for ≥ 3 months)
7. Contraception: Female patients must be postmenopausal, surgically sterile, or if premenopausal (and not surgically sterile), be prepared to use ≥ 1 effective method of contraception during the study and for 30 days after the end of treatment visit. Effective methods of contraception are considered to be those listed below:
 - Barrier method, ie, (a) condom (male or female) with spermicide **or** (b) diaphragm with spermicide; or

- Intrauterine device; or
 - Vasectomy (partner); or
 - Hormonal (eg, contraceptive pill, patch, intramuscular implant or injection); or
 - Abstinence, if in line with the preferred and usual lifestyle of the patient (where abstinence is defined as refraining from heterosexual intercourse)
8. Must provide written informed consent and agree to comply with the study protocol.

8.3. Patient Exclusion Criteria

1. Non-cirrhotic or cirrhotic CP-A (Mild; Score 5 to 6)
2. History of liver transplant or organ transplant
3. History of alcohol or drug abuse within 12 months prior to Screening
4. Current hepatic encephalopathy (as defined by a West Haven score of ≥ 2 [[AASLD, EASL 2014](#)])
5. History or presence of other concomitant liver diseases including:
 - a. Hepatitis C virus infection and RNA positive
 - b. Active hepatitis B infection; however, patients who have seroconverted (hepatitis B surface antigen and hepatitis B e antigen negative) may be included in this study after consultation with the Medical Monitor
 - c. Primary sclerosing cholangitis
 - d. Alcoholic liver disease
 - e. Definite autoimmune liver disease or overlap hepatitis
 - f. Gilbert's Syndrome
6. In the opinion of the Investigator, fluctuating or rapidly deteriorating hepatic function prior to randomization
7. Patients with history or presence of hepatorenal or hepatopulmonary syndrome
8. Patients with significant active infection (ie spontaneous bacterial peritonitis)
9. Patients with known or suspected hepatocellular carcinoma
10. History of known or suspected clinically significant hypersensitivity to OCA or any of its components
11. Participation in another investigational product, biologic, or medical device study within 30 days prior to Screening. Participation in a previous study of OCA is allowed with 3 months washout prior to enrollment in this study
12. Mental instability or incompetence, such that the validity of informed consent or ability to be compliant with the study is uncertain
13. UDCA naïve (unless contraindicated)
14. Known history of human immunodeficiency virus infection

15. Treatment with commercially available fibrates or participation in a previous study involving fibrates within 3 months before Screening, or plans to use commercially available fibrates during the study
16. If female: plans to become pregnant, known pregnancy or a positive urine pregnancy test (confirmed by a positive serum pregnancy test), or lactating

8.4. Dose Adjustment, Interruption, and Withdrawal from Investigational Product or Study

Investigational product may be temporarily decreased (eg, from 10 mg twice weekly to 5 mg twice weekly, or from 5 mg twice weekly to 5 mg once weekly) or temporarily or permanently stopped based on tolerability concerns. Investigational product may be resumed at the maintenance dose upon resolution of gastroenteritis or worsening renal function or dehydration if there is no evidence of liver injury. For rechallenge following all other dose interruptions (see Table 5), investigational product should be initiated at a lower dose and patients monitored more frequently with up-titration considered based on tolerability.

Adjustments, interruptions, discontinuation, and any rechallenge of investigational product should be implemented per the criteria outlined in Table 5. Patients that discontinue investigational product are expected to continue in the study (and follow the regular visit schedule, with the exception of PK sampling [trough PK may be required in the event of an AE consistent with hepatic injury or decompensation]) until the end of the study, but may withdraw consent at any time.

Table 5: Criteria for Dose Adjustment, Interruption, Discontinuation, and Rechallenge

DOSE ADJUSTMENT		
Criteria	Action Taken with IP	Adjustment
New Onset Severe Pruritus	Drug holiday or less frequent dosing	Return to original dose regimen if tolerated
DOSE INTERRUPTION		
Criteria	Action Taken with IP^a	Rechallenge^b
If liver biochemistries indicative of suspected hepatic injury are identified as exceeding upper threshold criteria and require immediate interruption (see Part A of Table 3) ^c	Interrupt immediately upon initial observation	Patient may be rechallenged after a minimum of 30 days if fully resolved OR stable and approved by the Medical Monitor and Investigator.
Other liver biochemistries indicative of suspected hepatic injury are outside upper threshold criteria upon repeat testing as defined in Part A of Table 3 ^d	Interrupt after confirmation by repeat testing	
Liver biochemistries indicative of potential hepatic decompensation in the absence of symptoms (see Part B of Table 3) ^e	Closely monitor until normalization or stabilization. If values continue to increase relative to the baseline value, interrupt	

Clinical events indicative of hepatic decompensation (see Part B of Table 4)	Closely monitor until normalization or stabilization	The patient may be rechallenged after a minimum of 30 days if fully resolved OR stable and approved by the Medical Monitor and Investigator. IP should be re-initiated at a lower dose (or lower dose frequency) and titrated per Investigator discretion.
Gastroenteritis (established severe abdominal pain, vomiting, diarrhea for more than 4 days)	Interrupt	If no evidence of liver injury is detected, IP may be restarted at the same dose after resolution of intercurrent illness.
Evidence of worsening of renal function or dehydration	Interrupt	
DOSE DISCONTINUATION		
Criteria	Action Taken with IP	Rechallenge
If INR increases ≥ 2.0 in absence of clinical symptoms criteria (unless due to vitamin K deficiency) ^f	Discontinue / No Rechallenge	Discontinue IP permanently and continue to return for scheduled study visits for safety follow-up.
If total bilirubin thresholds (Part B of Table 3) are observed in the presence of clinical symptoms of cholestatic hepatitis or hepatic encephalopathy ^f		Continue to return for scheduled study visits for safety follow-up. Monitor closely for clinical outcomes according to protocol assessments.
Multi-Organ failure requiring hospitalization		
Liver transplantation		
Pregnancy		

Fully resolved = Return to baseline levels or return to within normal limits (WNL). IP = investigational product

^a If patient is unable to be evaluated promptly, study drug must be immediately interrupted.

^b Requires complete documentation of complete resolution or normal/baseline results based on laboratory parameters and symptoms.

^c Total bilirubin baseline \leq ULN and $\geq 3x$ baseline, baseline $>$ ULN and $\geq 2x$ baseline, ALT or AST $> 3x$ baseline (and $>$ ULN)

^d ALT or AST $\geq 2x$ baseline or electrolytes (sodium $<$ 130 mEq/L).

^e Total bilirubin baseline \leq ULN and 1.5 mg/dL increase from baseline OR baseline $>$ ULN and 1.0 mg/dL increase from baseline; INR $>$ 0.3 increase from baseline

^f If INR increases ≥ 2.0 in the absence of clinical symptoms or if or total bilirubin thresholds OR an INR increase from baseline of ≥ 1.5 are observed in the presence of clinical symptoms of cholestatic hepatitis or hepatic encephalopathy.

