Total Bilirubin	Closely monitor until normalization or stabilization. If values continue to increase relative to the baseline value, interrupt IP.	The patient may be rechallenged after a minimum of 30 days if fully resolved OR stable and approved by the Medical Monitor and Investigator. If laboratory values do not normalize, IP should not be restarted.
Baseline \leq ULN and 1.5 mg/dL increase from baseline Baseline $>$ ULN and 1.0 mg/dL increase from baseline		
INR^b	Closely monitor until normalization or stabilization. If values continue to increase relative to the baseline value, interrupt IP.	The patient may be rechallenged after a minimum of 30 days if fully resolved OR stable and approved by the Medical Monitor and Investigator. If laboratory values do not normalize, IP should not be restarted.
$>$ 0.3 increase from baseline		
\geq 2.0 unless due to vitamin K deficiency	Discontinue IP permanently	Continue to return for scheduled study visits for safety follow up. Monitor closely for clinical outcomes per protocol.
Laboratory Criteria for Monitoring Potential Hepatic Decompensation in the Presence of Clinical Symptoms		
Total bilirubin thresholds defined in Part B OR an INR increase from baseline of \geq 1.5 are observed in the presence of clinical symptoms of cholestatic hepatitis or hepatic encephalopathy ^c	Discontinue IP permanently	Continue to return for scheduled study visits for safety follow up. Monitor closely for clinical outcomes per protocol.

IP = investigational product

^a Sodium will be measured as an assessment of liver failure (hyponatremia).

^b Does not apply in patients on anti-coagulants.

^c Symptoms of cholestatic hepatitis includes dark urine and jaundice. Symptoms of hepatic encephalopathy may include lack of awareness, shortened attention span, lethargy, gross disorientation, or coma (unresponsive to verbal or noxious stimuli).

It should be noted that it is difficult to recognize every potential marker of hepatic or renal deterioration. There is no substitute for good medical judgment. Investigators will be reminded to be cautious and mindful in their evaluation of patients' symptoms, signs, and laboratory results. However, for example, a single abnormal laboratory analyte result may be artefactual; accordingly, Investigators will be allowed to implement an alternate follow-up procedure if considered appropriate based on their medical judgement, but only after documented agreement with the Sponsor's Medical Monitor.

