7.4.3. Clinical Criteria for Monitoring for Potential Hepatic Decompensation

Patients will be monitored for potential hepatic decompensation events throughout the study. Clinical criteria for monitoring these events and the interruption/discontinuation of investigational product is summarized in [Table 4](#).

Investigational product should be discontinued permanently if the patient received a liver transplant or experiences multi-organ failure as defined in Table 4, Part A. Patients should continue to return for scheduled study visits for safety follow-up.

Patients who experience other potential hepatic decompensation events defined in Table 4, Part B should be closely monitored until normalization or stabilization. Patients may be rechallenged after a minimum of 30 days if fully resolved OR stable and approved by the Medical Monitor and Investigator.

Table 4: Clinical Criteria for Monitoring Potential Hepatic Decompensation Events and Interruption / Discontinuation of Investigational Product

Hepatic Decompensation Events Requiring Mandatory Discontinuation of Investigational Product	
Decompensation Event	Action Taken / Rechallenging Criteria
Liver Transplant Multi-organ failure requiring hospitalization	Discontinue IP permanently and follow patients until normalization/stabilization. Continue to return for scheduled study visits for safety follow up.
Hepatic Decompensation Events Requiring Interruption of Investigational Product	

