
 1. Liver failure defined as worsening synthetic function that is persistently worse relative to baseline and/or progressive over time (see Table 3, Part B)^a 2. Variceal bleeding or recurrent variceal bleeding^b documented by endoscopy or accompanied by anemia or melena with a hemoglobin drop of ≥ 2 g/dL 3. Ascites^c including: 
 1. Worsening – requires increase in drug therapy or surgical intervention (paracentesis or shunt procedure) 2. Refractory ascites – unresponsive to medication; patient not candidate for transjugular intrahepatic portosystemic shunt (TIPS) or shunt; requires large volume paracentesis 3. Hyponatremia (≤ 125 mEq/L) secondary to ascites 1. Spontaneous Bacterial Peritonitis 2. Hepatic Encephalopathy, Grade ≥ 2 3. Any liver-related event requiring hospitalization and treatment (except multi-organ failure) 4. Hepatorenal syndrome Type 1 or Type 2 and acute kidney injury, hepatopulmonary syndrome, or portopulmonary syndrome 	
Closely monitor until normalization or stabilization.
 
The patient may be rechallenged after a minimum of 30 days if fully resolved OR stable and approved by the Medical Monitor and Investigator
 
IP should be re-initiated at a lower dose (or lower dose frequency) and titrated per Investigator discretion.

^a Patients experiencing INR ≥ 2.0 unless due to vitamin K deficiency should be discontinued from IP permanently without rechallenge and should to return for scheduled study visits for safety follow up.

^b Endoscopic confirmation of gastric or duodenal varices without evidence of bleeding should be closely monitored; investigational product may be interrupted at Investigator discretion

^c New onset ascites requiring treatment should be closely monitored; investigational product may be interrupted at Investigator discretion

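### The INR rule for permanent stopping is a value in Tables 3 and 4 but an increase in Table 5; if the value applies, entry criteria admit patients who already meet it on Day 1

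*Protocol*

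**What the plan says.** **INR, permanent stop.** In the Table 3 block for patients without clinical symptoms (Section 7.4.2), product is discontinued permanently at an INR of at least "2.0 unless due to vitamin K deficiency". Table 4 footnote a (Section 7.4.3) likewise refers to patients with an INR of at least "2.0 unless due to vitamin K deficiency should be discontinued from IP permanently without rechallenge". Table 5 (Section 8.4) makes the trigger an INR that increases, with the figure given as at least "2.0 in absence of clinical symptoms criteria (unless due to vitamin K deficiency". Footnote f to Table 5 repeats the increase wording and runs on to the symptomatic rule in the same sentence: "2.0 in the absence of clinical symptoms or if or total bilirubin thresholds OR an INR increase from baseline of" at least 1.5.

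**Exemptions and symptomatic limb.** All three tables carry the vitamin K exemption. The exemption for patients on anticoagulants is a footnote to the INR entry of Table 3 only. Table 3 gives the symptomatic rule as either a bilirubin threshold or an INR rise of 1.5. The Table 5 row for symptomatic patients names bilirubin only, and its INR limb appears only in footnote f.

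**Which table governs.** Section 7.4 points to Sections 7.4.2 and 7.4.3 (Tables 3 and 4) for interruption and discontinuation. Section 8.4 tells sites to implement Table 5. No order of precedence is given.

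**Entry.** Section 8.2 requires a Child-Pugh score of 7 to 12 and a "MELD score of 6 to 24 at Screening". Neither Section 8.2 nor 8.3 caps INR.

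**Table 4 Part B events.** The block is headed "Hepatic Decompensation Events Requiring Interruption of Investigational Product". Its action cell opens "Closely monitor until normalization or stabilization" and contains no instruction to interrupt. Table 5 places "Clinical events indicative of hepatic decompensation (see Part B of Table 4" under its dose-interruption heading with the same monitoring-only action, and the text of Section 7.4.3 also says only to monitor.

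**The concern.** These are mandatory hepatic stopping rules in a population that Section 5.5 describes as being at elevated risk of decompensation. If two sites can read the same INR result under different rules, discontinuation and exposure will partly reflect the table each site followed. Both feed the primary safety and PK objectives.

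The overlap with entry adds a second issue. A patient dosed on Day 1 belongs to the ITT and Safety Populations (Section 15.1). Serial PK sampling starts at Week 12 (Section 12.1), and patients who discontinue product leave the PK sampling schedule, apart from a possible trough sample after a hepatic event (Section 8.4). Anyone stopped before Week 12 therefore gives no serial profile.

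**Working it through.** The protocol states no figure to reproduce on this point. The check compares the rules and then tests whether entry and permanent stop can both be met.

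**1. INR level at which each wording triggers.** Value rule: 2.0. Symptomatic rule: baseline + 1.5. Table 5 read literally: baseline + 2.0.

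| Baseline INR | Value (Table 3; Table 4 footnote a) | Symptomatic rise of 1.5 (Table 3; Table 5 footnote f) | Rise of 2.0 (Table 5; footnote f) |
|---|---|---|---|
| 1.2 | 2.0 | 2.7 | 3.2 |
| 1.5 | 2.0 | 3.0 | 3.5 |
| 1.8 | 2.0 | 3.3 | 3.8 |
| 2.0 | already met | 3.5 | 4.0 |

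At baseline 1.5 the value and the literal rise differ by 3.5 − 2.0 = 1.5 INR units.

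**2. Can an INR of 2.0 or more satisfy the MELD limit?** The current text prints no MELD formula. Section 13.2.6 names the components (creatinine, bilirubin, INR) and a United Network for Organ Sharing modification. As an assumption I use the formula shown in Appendix B as superseded text:

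MELD = 3.78 ln(bilirubin) + 11.2 ln(INR) + 9.57 ln(creatinine) + 6.43, with bilirubin and creatinine in mg/dL.

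- Bilirubin 3, INR 2.0, creatinine 1.0: 4.15 + 7.76 + 0 + 6.43 = 18.3.
- Bilirubin 3, INR 2.5, creatinine 1.0: 4.15 + 10.26 + 0 + 6.43 = 20.8.
- INR 2.0 across bilirubin 1 to 8 and creatinine 0.8 to 1.2 (values below 1.0 set to 1.0): 14.2 to 23.8.

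All of these lie within 6 to 24.

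**3. Can the same patient satisfy the Child-Pugh limit?** Table 12 gives 2 points for INR 1.7–2.3 and 2 points for bilirubin 2.0–3.0 mg/dL, so the first example has 4 points. Albumin and ascites add 1 to 3 each. Encephalopathy adds 1 or 2, because exclusion 4 removes West Haven 2 and above. The total runs from 4 + 3 = 7 to 4 + 3 + 3 + 2 = 12, which is exactly the admitted range.

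**4. Does an exclusion catch this patient?** The nearest is exclusion 6, which concerns fluctuating or rapidly deteriorating hepatic function in the investigator's opinion. A stable INR of 2.0 does not meet it.

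**5. Dependence on the reading.** Under the value rule this patient meets permanent stop on Day 1. Under the literal Table 5 rule the Day 1 rise is zero and the rule is not met.

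**The case against.** **The Table 5 wording may simply be loose for an increase to 2.0.** Where Table 5 means a change, footnotes e and f say so by reference to baseline (the 0.3 and 1.5 figures). The 2.0 figure lacks those words, and two other places give it as a value. This is a fair argument about drafting intent. It does not settle the text: the increase wording occurs twice, footnote f joins it to an increase from baseline, and Section 8.4 makes Table 5 the table to implement.

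**A reader might infer that eligibility flatly admits patients who must stop on Day 1.** The documents do not support that unconditionally. It needs the value reading and excludes INR raised by vitamin K deficiency and, under Table 3, patients on anticoagulants. Section 7.4.2 also describes thresholds as prompting repeat tests and allows alternate follow-up after documented agreement with the Medical Monitor. Those provisions soften the consequence, but they presuppose a defined default rule.

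**A reader might infer that the rule is laxer for symptomatic patients,** because 3.0 exceeds 2.0 at baseline 1.5. That compares one limb only. The symptomatic rule also triggers on bilirubin rises of 1.0 or 1.5 mg/dL, and Table 4 footnote a is not limited to asymptomatic patients.

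**A reader might infer that the tables flatly disagree on interrupting versus monitoring Part B events.** Both headings say interruption, and the 30-day rechallenge at a lower dose or frequency presupposes it. Table 4 footnotes b and c make interruption discretionary only for lesser events, and Section 7.6 describes close monitoring as following interruption. What stands is an incomplete action cell. Neighbouring Table 5 rows do say to interrupt, and Table 3 uses close monitoring as a step before interruption, so the omission can mislead.

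**A reader might infer that such patients would fill the Child-Pugh C minimum without PK data.** The protocol gives no share of patients with a baseline INR of 2.0 or more, so this is speculation.

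**Conclusion.** The INR criterion for permanent discontinuation is inconsistent as written, with unequal exemptions and an INR limb missing from the symptomatic row of Table 5. The readings differ by 1.5 INR units at a baseline of 1.5. The overlap between entry and permanent stop is real but conditional on the value reading, outside the two exemptions. The MELD part of that check rests on the superseded formula, although the example scores of 18.3 and 20.8 sit well inside the limit of 24. The number of patients affected, and hence any loss of serial PK profiles, is unknown. The Part B action is a secondary repair of wording. No view is taken on which threshold or action is clinically right.

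**What to change.** - Reconcile Table 3, Table 4 footnote a, Table 5 and its footnote f to one wording of the INR criterion, stating whether 2.0 is a value or a change from baseline, with the same vitamin K and anticoagulant exemptions wherever it appears.
- Make the symptomatic row of Table 5 agree with its footnote and with Table 3 on the INR limb.
- State one action for Table 4 Part B events in Table 4, Table 5 and Section 7.4.3.
- Reconcile the resulting INR criterion with Sections 8.2 and 8.3, so that the protocol says what happens when a patient meets both entry and permanent stop.

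The clinical team decides the reading in each case. The cost is amendment text and a letter to sites, with no new assessments. If the reconciliation changes the entry criteria, it could narrow recruitment, which Appendix C gives as the reason for expanding from 35 to 50 sites. A count of patients at or above the stop value at baseline would be a useful optional addition to the SAP.
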